**1.0 Objectives**

The purpose of this research is to test quantitatively the effectiveness of the Life Story Work (LSW) intervention, with a book product (LSB), for reducing depression and increasing meaning in life (MIL) for mentally alert nursing home (NH) residents.

The overall objective is to improve the quality of life for residents of NHs by determining whether the LSB intervention will have a greater and longer lasting effect compared with care as usual (i.e., decreased depression and increased meaning in life).

Hypothesis I LSB will lead to greater reductions in depressive symptoms than care as usual.

**FULL PROTOCOL TITLE:** The Effectiveness of Life Story Book on Depression and Meaning in Life for Mentally Alert Residents of Nursing Homes

Hypothesis II LSB will lead to a greater increase in MIL than care as usual.

My central hypothesis, formulated from my preliminary research, is that the LSB intervention will improve the quality of life for mentally alert NH residents and will have longer lasting effects than care as usual. If effective, it may offer a non-pharmacological intervention for improving care and quality of life for NH residents.

## **2.0 Background**

Depression and lack of MIL are major concerns for residents of NHs. Residents have been shown to be at an increased risk for depression [1], [2]; with approximately 50% having a diagnosis of depression [3]. Although nearly half of NH residents are diagnosed with depression, depression still remains poorly recognized because it often co-occurs with other chronic medical conditions [3].

The consequences of depression can be devastating for residents which include decreased physical, cognitive and social functioning, greater self-neglect, and an increased risk of morbidity and the risk of suicide [4], [5]. In addition, untreated depression may result in the development of, or the worsening of, medical conditions [6].

Meaning in life has been shown to be a protective factor against depression [7]. Whereas a decrease in MIL has been shown to also have a relationship with deterioration of physical health, cognitive decline, and mortality [8], [9].

Pharmacological interventions for depression are the strategies that are typically used to treat depression in NHs. Furthermore, antidepressant medications have been shown to increase an older adults' risk for falls [10] and despite the many other undesirable side effects for older adults, they are often the first line of treatment for depression [11].

NH policies and programs have emphasized a medical model of care that has focused on quality of care and pharmacological interventions [12]. Unquestionably, quality of care is extremely important, but quality of life is also critical to health [13], [14], and non-pharmacological psychosocial interventions are often undervalued [15]. This common, long-standing practice of using antipsychotic medications is causing serious harm to these frail older adults [16], [17]. The Centers for Medicare & Medicaid Services has led a nationwide directive to reduce the use of antipsychotic medications [18].

The personalization of interventions that allow for exploring autobiographical memories, such as the reminiscence intervention LSB has been shown to have significant effects on depression and psychological well-being.

LSB is a reminiscence intervention designed to provide a person with the opportunity to review their past and capture their life story into something tangible. It involves another person listening and assisting the person to review and sometimes evaluate their life [19].

## **FULL PROTOCOL TITLE:** The Effectiveness of Life Story Book on Depression and Meaning in Life for Mentally Alert Residents of Nursing Homes

Each life story is recounted in chronological order, from childhood to their current age, and involves compiling the person's history, stories, information, photographs, texts, memorabilia, into something tangible [20], [21], [22]. This tangible product is then a reminder or visual aid of the individual's life history.

LSB's premise is that every person has a story - a personal history - with events, people, circumstances, actions, feelings, insights, thoughts, learning, and milestones that define who they are [23], [20], [24].

Previous studies for LSB for persons with dementia reported positive outcomes on aspects of cognition and mood [25], [26]. However, there is a gap in the literature regarding the effects of LSB on depression and MIL for residents of NHs who are mentally alert [27], [28]. Mentally alert residents of NHs, who make up almost 50% of the population of NHs, also need effective interventions that maintain their health and well-being.

Improving quality of care and quality of life for older adults living in NHs, while reducing the use of pharmacological interventions, is a critical need [18]. The proposed research has the potential to provide a non-pharmacological psychosocial intervention for reducing depressive symptoms and increasing meaning in life for mentally alert nursing home residents. This research is aligned with the mission of National Institute on Aging to support research related to the problems and needs of older Americans and to develop effective interventions that maintain their health and well-being [29].

### **3.0 Inclusion and Exclusion Criteria**

Two Medicare and Medicaid certified NHs, located in Harris and Fort Bend Counties, and freestanding, or ones that are not a part of a hospital or a continuing care retirement community, will be invited to participate in this research.

Residents of the two selected NHs, ages 57 and older and who have the ability to speak English, will be invited to complete an eligibility screening to participate in this study. Eligibility will be determined using the Six-Item Screener (SIS), as measured by a score of 4 or higher for cognitive impairment.

**The Six Item Screener (SIS)** was specifically developed from the Mini-Mental State Examination (MMSE) to screen subjects for cognitive ability to participate in research studies. The SIS was found to have good test-retest reliability (.705), internal consistency (.82) and sensitivity (.90) [29]. The scale is unobtrusive, only takes 1-2 minutes to complete and can easily be incorporated into the initial eligibility assessments [30]. (*Please see attached screener*).

Exclusion criteria will consist of residents who scored less than 4 on the SIS, indicating cognitive impairment; individuals who do not speak English; and individuals who are not residents of the participating NH.

**FULL PROTOCOL TITLE:** The Effectiveness of Life Story Book on Depression and Meaning in Life for Mentally Alert Residents of Nursing Homes

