## **5.0 Number of Subjects**

Two nursing homes will be recruited for comparison of LSB with care as usual. A power analyses for a MANOVA, with 2 groups and 2 dependent variables, was conducted in G\*Power Version 3.1.9.2 [32] to determine a sufficient sample size. Using an alpha ( $\alpha$ ) of .05, and a large effect size of  $d = .94$  [33], a sample size of 20 could achieve a power of 95% to detect between group differences.

Prior research in long-term care facilities indicates that oversampling by 15-20 percent is an efficient way to deal with attrition. This study will recruit 24 residents, or 12 residents per NH, to ensure a sample size of 20. From these two NHs, a minimum of 20 NH residents (10 per NH) and a maximum of 24 NH residents (12 per NH) will be recruited.

**FULL PROTOCOL TITLE:** The Effectiveness of Life Story Book on Depression and Meaning in Life for Mentally Alert Residents of Nursing Homes

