### *Description of all research procedures being performed and when they are performed:*

After identifying potential participants, private informational meetings with the research team which will include the PI and two research assistants -will be conducted with each potential participant where initial screening, using the SIS, will be administered by the PI. (*Please see attached screening script/tool*). If the resident is eligible, and would like to participate, the research team will further explain the study, including the length of the study-10 weeks with six visits, length of the visits 1- hour, three weeks with no visits, and the measures that will be

**FULL PROTOCOL TITLE:** The Effectiveness of Life Story Book on Depression and Meaning in Life for Mentally Alert Residents of Nursing Homes

collected. Full disclosure and written consents will be explained with plenty of time for any questions or clarification before consent forms are signed. The consent form will include the purpose, procedures, risks and costs of participating in the LSB. Again, there will be no costs for participating in the study and the research team will receive no monetary income from the LSB. In addition, the LSB will be the property of the participant, along with any scanned photos or stories written. This will be signed by each participant, each RA, and the PI. A copy of the consent form will be given to each participant. Additional information will be provided for those participants who would like to request their family's cooperation to secure photos and/or memorabilia. (*See attached information sheet*).

Although the recruitment of participants is for mentally alert residents, if they have given durable power of attorney to others, it may be necessary, per their NH regulations, to obtain informed consent from their designated durable powers of attorney [35], [36], [37]. The durable power of attorney will be contacted, permission sought, and the consent form signed. The consent form will also include an agreement that the LSB ownership will be with the participant. [38] A copy of the consent form will be given to the durable power of attorney.

Participants will be notified for scheduling of the LSB intervention, by their preferred method of notification, once recruitment is completed. When participant recruitment levels are met, the research team will contact the participants to schedule their first visit. LSB visits for all participants will begin the same week.

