At the first visit the PI will administer the following instruments in face-to-face interviews with each screened participant. Residents' characteristics measures will include socio-demographic data and a functional status survey. The socio-demographic data that will be collected for each participant will include: year born, gender, marital status, level of education, ethnicity, religion, and length of residence in the NH. (*Please see attached instruments*).

**FULL PROTOCOL TITLE:** The Effectiveness of Life Story Book on Depression and Meaning in Life for Mentally Alert Residents of Nursing Homes

**Katz Index of Independence in Activities of Daily Living** (ADLs) will be administered in order to assess the functional status of the participant's ability to perform activities of daily living independently. This tool is one of the most commonly used tool to measure an older adult's functional status. The Index ranks the adequacy of performance in six areas of function: bathing, dressing, toileting, transferring, continence, and feeding. Persons are scored yes/no for independence in each of the six functions. A score of 6 indicates full function, 4 indicates moderate impairment, and 2 or less indicates severe functional impairment. The instrument is used effectively among older adults in the community and all care settings. This is a scale of the six activities of daily living [42].

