[name] is an Assistant Professor at the University of Houston College of Nursing and named a 2018 Salute to Nurses Top 15 winner. She has served as an oncology nurse for 37 years and is certified in gerontology. In addition, [name] is a certified instructor for Reminiscence and Life Story Work. She will serve as a consultant on this study.

The two NHs that will be recruited will be described upon their consent and letters of cooperation will be obtained. The NHs will be comparable on the following five aspects: number of long-stay residents, overall quality rating, staff rating, type of ownership (private, public or government) and facility size. Each of the NHs participating in this study will have a minimum of 85 residents. According to the Vital Statistics report- *Long-Term Care Services in the United States: 2013 Overview*, there are about 49.6% of NH residents who are mentally alert [3]. With approximately 50% of NH residents being mentally alert, there will be approximately 42 residents to recruit from the NHs that house 85 residents.

Two social work/medical professionals will be hired as research assistants. Once they are hired, I will submit an IRB modification with their information.

An IRB modification with the two site coordinators information, along with the nursing home letters of cooperation, will be added.

Recruitment will begin immediately upon IRB approval and will continue until the minimum of 10 and maximum of 12 participants from each NH (Total 20 minimum and 24 maximum) are recruited. Transcription will begin immediately after each LSB visit with participants and data will be analyzed after all data collection is complete. We anticipate that we will be able to complete the intervention three months following IRB approval. The LSB intervention and analyses should be completed within six months following IRB approval.

**FULL PROTOCOL TITLE:** The Effectiveness of Life Story Book on Depression and Meaning in Life for Mentally Alert Residents of Nursing Homes

Adequate psychological and/or medical resources are available and can be provided by the NHs for those who may need it as a result of an unanticipated consequence of research participation.

The research team will communicate on an ongoing weekly basis to discuss any issues that may arise so as to ensure successful execution of this research study. All of the key personnel listed in this study have read and understand this protocol.

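### Section 3.0 has no criterion on planned discharge, so a resident already due to leave within the 10-week course can enrol and be lost to the post-tests

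*Combined protocol and SAP*

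**What the plan says.** **Entry.** Section 3.0 opens screening widely: "Residents of the two selected NHs, ages 57 and older and who have the ability to speak English, will be invited to complete" the screener. The cognitive rule follows: "Eligibility will be determined using the Six-Item Screener (SIS), as measured by a score of 4 or higher". The exclusions are a score below 4, not speaking English, and "individuals who are not residents of the participating NH". Nothing is asked about expected stay.

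**Homes.** Section 29.0 says that the two homes will be comparable on five aspects, beginning with "number of long-stay residents, overall quality rating, staff rating". It estimates a pool of about 42 per home by applying roughly 50% mentally alert to all 85 residents.

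**Timing.** Section 10.0 has residents told before consent that the study runs "10 weeks with six visits". Section 8.0 starts the course only when recruitment levels are met. NH-B has its first post-test at 4 weeks, under usual care until then, and receives LSB afterwards. NH-A has an additional post-test after one month to look at lasting effects.

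**Measurement and loss.** The measures are administered face to face (Section 10.0), and the intervention is delivered at the homes (Section 11.0). Baseline data include "level of education, ethnicity, religion, and length of residence in the NH", collected at the first visit, after consent. Section 5.0 states that "oversampling by 15-20 percent is an efficient way to deal with attrition" and recruits 24 to secure 20. Section 25.0 records reasons for withdrawal and loss, but gives no method for missing outcomes.

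**The concern.** The plan treats long-stay status as relevant to choosing homes, yet asks nothing about stay when choosing people. A resident whose discharge or transfer is already arranged for, say, three weeks after the first visit meets every criterion. Early recruits face a longer wait still, because the course does not begin until both homes are full.

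Such a loss could be seen at screening, and analysis cannot recover a post-test that was never taken. It uses an allowance meant for losses that cannot be foreseen, such as illness or refusal. In NH-B, a resident who leaves by week 4 receives no LSB sessions, although Section 10.0 defends the design on the ground that everyone will eventually receive the intervention.

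**Working it through.** **1. Is such a resident eligible?** The Section 3.0 requirements are residency, age 57 or over, English, and a screener score of 4 or higher. None depends on the date of leaving. Length of residence looks backward and plays no part in eligibility. The answer is yes.

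**2. Which analyses lose the person?**

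| Time of leaving | NH-A | NH-B |
|---|---|---|
| Before post-test 1 | Lost to the MANCOVA and to the lasting-effect check | Lost to the MANCOVA; no LSB sessions (post-test at 4 weeks) |
| Between post-tests 1 and 2 | Lost to the lasting-effect check | Lost to the LSB phase |

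Section 25.0 does not name the time point of the MANCOVA. The contrast of LSB with usual care exists only at post-test 1, because both homes have been offered LSB by post-test 2.

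**3. The plan's own figure.** Inputs from Section 5.0: two groups, two outcomes, alpha .05, effect size .94, N = 20, power 95%. Two-group MANOVA power comes from the noncentral F with 2 and N − 3 degrees of freedom and noncentrality λ = N × f².

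- Entering .94 as f² gives λ = 20 × 0.94 = 18.8 on 2 and 17 degrees of freedom, and power 0.952. The stated 95% is reproduced.
- On the same basis, power is 0.923 with 18 completers and 0.878 with 16.

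Section 5.0 labels .94 as *d*, and the figure reproduces only when it is entered as f². That is a separate matter on which this point does not rest.

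**4. The allowance.** 24 − 20 = 4 losses, and 4/24 = 16.7%. Section 5.0 also permits recruitment to stop at 20, in which case there is no allowance.

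**5. How sensitive is the allowance?** Let q be the probability that an enrolled resident is lost for any reason, independently of the others. The documents do not give q, so a range is assumed. Fewer than 20 completers means 5 or more losses: P(X ≥ 5), with X ~ Binomial(24, q).

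| Assumed q | Expected completers, 24 × (1 − q) | Chance of fewer than 20 |
|---|---|---|
| 10% | 21.6 | 8.5% |
| 15% | 20.4 | 28.7% |
| 20% | 19.2 | 54.0% |
| 30% | 16.8 | 88.9% |

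**6. What the table does not show.** q covers death, illness, refusal and every kind of departure. The documents give no share of short-stay residents, no discharge rate and no background loss. The part of q that the fix would remove is therefore unknown. The table shows only that a few additional losses matter with 24 enrolled.

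**7. Pool.** 85 × 0.496 = 42.2 per home, and 12/42.2 = 28%. This pool counts all residents, including any who would be excluded by a stay criterion, by age or by language.

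**The case against.** The strongest reply is that the plan already has partial safeguards. Residents hear the length of the study before they sign. All visits are scheduled at the first visit. The home's administration helps to identify candidates, and reasons for loss are recorded. A resident with a fixed leaving date would probably notice the conflict. The screening script is an attachment and is not in the text available, so its questions cannot be checked. This lowers the likely number of such enrolments, but none of it is an entry rule, and informal selection by staff could differ between the two homes.

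A second reply is that oversampling covers attrition. It covers up to 4 losses of 24, and falling slightly short is not a cliff: on the plan's own basis, 18 completers still give 0.923. That stands, and it limits the seriousness. Oversampling does not supply the missing post-tests or NH-B's missed LSB sessions.

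Four stronger readings are tempting and are not supported:

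- *The plan fails if either home loses 3 of 12.* Section 5.0 protects a total of 20. Its figure of 10 per home is a recruitment minimum, not a completer requirement. Losing 3 in one home and none in the other leaves 21.
- *The hypotheses rest on post-test 2.* Hypotheses I and II compare LSB with usual care, which is the post-test 1 contrast. Post-test 2 carries the lasting-effect aim and the second implementation, for which no power is claimed.
- *Those who leave differ in function and mood, so the groups are no longer comparable.* No section says so, and the comparability in Section 29.0 is between facilities.
- *Entry should be limited to long-stay residents.* The term is not defined in the documents, and the restriction is not needed to prevent foreseeable loss.

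**Conclusion.** The gap is real: nothing in Section 3.0 stops enrolment of a resident already known to be leaving before the last post-test, and no follow-up after discharge is described. Departure before post-test 1 costs the main comparison, and later departure costs the lasting-effect check or NH-B's LSB phase.

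Its size cannot be derived from the documents. The range of 8.5% to 88.9% for fewer than 20 completers rests on assumed all-cause loss of 10% to 30%, independent losses and the full 24 enrolled. It illustrates how thin the allowance is and does not estimate the effect of planned discharge. The required sample size is unchanged at 20 evaluable and 24 enrolled. This is an inexpensive improvement to make before enrolment, not a flaw that invalidates the design.

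**What to change.** Add to Section 3.0: *no discharge or transfer from the home planned before post-test 2 (within 10 weeks of the first visit)*. Ask it at the existing 10-minute screening. Because the course waits for recruitment to fill, reconfirm it at the first visit before the pre-test. Restate the pool in Section 29.0, since the figure of about 42 counts all residents.

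The cost is one question and a sentence of protocol text. The pool becomes smaller by an amount the documents do not give, so the 28% needed per home (12 of about 42) is a lower bound. Results will apply to mentally alert residents expected to remain in the home through the course, which is somewhat narrower than the population named in Section 1.0 and should be stated when the results are reported.

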## **4.0 Vulnerable Populations**

Mentally alert residents of the two NHs are eligible to participate in this study with safeguards included to protect the welfare, safety, privacy and confidentiality of this vulnerable population.

The NH administration will assist in identifying potential participants, but the research team will assure the residents that participation is completely voluntary, and that refusal to participate will not compromise their relationship with the staff or their care.

Due to institutionalization residents are more susceptible to coercion. There is the potential that residents may feel that they cannot refuse participation when asked by staff, due to the fact that residents depend upon that staff for food shelter, health and social services [31]. Again, assurances by the research team will be made that participation is completely voluntary and that they may decline participation.

Using the SIS for screening eligible also ensures that the participants have the cognitive ability to understand what will happen in the research, what risks may be involved, and that participation is voluntary. In addition, the research team will conduct all eligibility screening in private and the results of the SIS will be kept confidential and will not be shared with the potential participant or the NH staff. Potential participants who do not meet the inclusion criteria will be informed that for this study they are not eligible. No identifying information will be collected from them.

All scoring of instruments administered will be kept confidential and will not be shared with the NH staff.

Residents may have hearing or vision problems and may therefore require more time to have the study explained to them. Information flyers and informed consents will be read to the residents, along with using larger font.

Although this population is vulnerable, this research proposes minimal risk and will directly benefit participants in providing them with a life story book of their own and has the potential to reduce depressive symptoms and increase MIL.

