**6.0      Recruitment Methods**

Upon IRB approval, the two NHs will be contacted by telephone and email to provide follow-up information about this research study, its objectives and their role in recruitment. (*Please see attached*). A meeting will be scheduled with the request to meet as many of the NH's management team as possible. For these face-to-face meetings informative flyers with background information and simplified research procedures will be provided. (*Please see attached*). In addition, every effort will be made to recognize the NH's contribution to the study including: a plaque for participation, a presentation of the results of the study, and an LSB toolkit donated for continued use with other residents. This toolkit will include: portable scanner, scrapbook albums, audio recorder, USB flash drives and pad and pens.

NH administrators will be asked for the name of a staff member who might serve as an on-site point of contact. This site coordinator would be the research team's point of contact for scheduling, data collection and other communication between the research team, participants and the facility. NH staff have many demands for their time, so this site coordinator will be offered a stipend of \$300.00; \$150.00 halfway through the data collection (or at post-test 1) and \$150.00 when the data collection is complete (or at post-test 2).

Non-probability voluntary sampling method will be used to recruit participants from these two NHs. The NH administration, together with the PI, will identify potential participants. If there is an active resident council at the NH, this group may be contacted in order to introduce the study and recruit potential participants. Every NH, certified by Medicare and Medicaid, must provide a space for councils to meet. Resident councils are a group of residents that meet on a regular basis to discuss concerns, provide suggestions and plan activities for the NH [34].

Additional information meetings will be arranged, as needed, with the assistance of the NH administration, to describe the study and to answer residents', staff, and any family members' questions. (*Please see attached information flyer*).

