## **15.0 Provisions to Monitor Data to Ensure the Safety of Subjects**

This is a minimal risk study.

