## **19.0 Confidentiality**

Provisions will be made to protect all identifiable data in order to protect the privacy and maintain the confidentiality of all participants from recruitment to maintaining the data. These provisions will include the confidentiality of residents who did not meet the eligibility criteria; de-identification of each participant with a study number; a database created and files secured with passwords used only by the research team; components of the study data will be kept in a locked file cabinet; the research team will be well trained in how to maintain participant

**FULL PROTOCOL TITLE:** The Effectiveness of Life Story Book on Depression and Meaning in Life for Mentally Alert Residents of Nursing Homes

confidentiality; and the research team will have completed the required CITI training on ethical conduct of research. To ensure privacy, written agreements between the research team and the participants will be signed to ensure that no stories will be included in their LSB that do not have the express permission of the participants. The LSB will belong to the participant and any information or stories shared will not be disclosed to families or staff to protect the participant. (*Please see attached*).

**Paper Documentation of Screeners, Study Instruments and Receipt:** Eligibility screeners, consent documents, and documentation for receipt of the completed LSB will contain participants names (not ID numbers), and they will be kept separate from all other study information in a locked filing cabinet in the PI's office (345A SOCW). The code book with the name and the ID number of the participant will be kept in a separate locked filing cabinet in SOCW room 333, and will be destroyed following data collection. Completed study instruments will only contain the participants' ID number and will be kept on an encrypted and password protected file on the UH SharePoint site. Any data or documentation relating to this study will not be accessed by anyone but the research team.

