**20.0 Provisions to Protect the Privacy Interests of Subjects**

Participants will be provided with some examples of the *Life Review and Experiencing Form* questions as part of the informed consent process; in addition to the purpose of the

study and the necessity of disclosing some personal information. This will be clearly explained as part of the consent process. Participants will be informed that only the research team will have access to the LSB intervention transcripts and survey instruments. Participants will also be informed that they can refuse to answer any question or withdraw from the study at any time, without penalty, and without giving a reason for withdrawing from the study.

All survey instruments will be administered by the PI, a licensed master social worker who has experience working with older adults in nursing homes. The LSB intervention will be conducted by two social work/medical professionals who will be provided training, by the PI, for working with older adults in nursing homes. In addition, participants can ask questions about their participation in the research process at any time.

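### The protocol body gives no exception to confidentiality, and no route to nursing home clinicians, if a resident voices a suicidal thought or intent to self-harm

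*Combined protocol and SAP*

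**What the plan says.** Three places in the protocol limit what leaves the research team.

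- Section 4.0, on scores: "All scoring of instruments administered will be kept confidential and will not be shared with the NH staff".
- Section 19.0, on what residents say: "any information or stories shared will not be disclosed to families or staff to protect the participant".
- Section 20.0, on what residents are told: "Participants will be informed that only the research team will have access to the LSB intervention transcripts and survey instruments".

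None carries an exception for risk of harm. The whole of section 15.0, on monitoring for safety, reads "This is a minimal risk study". Section 9.0 sets no safety endpoints.

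The protocol does have general safeguards. Under 13.0 and 20.0 the PI, a licensed social worker, gives every instrument. The PI also trains and supervises the RAs, including on painful memories, and the homes have psychological services on site. Section 29.0 adds that psychological or medical help "can be provided by the NHs for those who may need it as a result of an unanticipated consequence of research participation".

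**The concern.** Section 2.0 describes depression in nursing home residents as under-recognised and lists suicide among its risks. The trial interviews such residents about mood three times and leads them through a review of their whole lives. A resident may voice a suicidal thought or an intent to self-harm in either setting.

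If that happens, the people able to act are the home's clinicians. A team member who follows 19.0 to the letter would keep the statement from them. One who speaks up would be acting outside what 19.0 says, and without residents having been told of any such limit in the terms that 20.0 sets out. Resident safety is at stake first, and the accuracy of the consent discussion second.

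**Working it through.** The plan gives no figure to reproduce and no arithmetic applies. The check is to take one event and follow it through the text.

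**Event.** A resident voices a suicidal thought to an RA during a Life Story Book session. Section 10.0 has the RAs conduct these sessions, and nothing places the PI at them, so the RA may be the only team member who hears it.

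**Step 1: do the confidentiality statements cover it?**

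- 4.0: no. A spoken statement is not a score, and a referral need not mention one.
- 20.0: not directly. It concerns access to transcripts and instruments, and naming a concern opens neither. But it tells residents of no limit.
- 19.0: yes, on its literal wording, which reaches any information shared and names staff. The neighbouring sentences are about the book, so a narrower reading is possible, but the sentence does not confine itself to the book.

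**Step 2: does any other text supply the route?**

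| Section | What it offers | What it leaves open |
|---|---|---|
| 15.0 | A risk classification | Everything: no procedure |
| 13.0 | Trained, supervised RAs; services on site | Trigger, timing, permission to tell staff |
| 29.0 | Resources that the homes can provide | Trigger, responsible person, timing, permission to tell staff |
| 6.0 | A site coordinator, "the name of a staff member who might serve as an on-site point of contact", who handles "other communication between the research team, participants and the facility" | No safety use is stated, and the coordinator is staff, so the literal 19.0 wording applies |
| 29.0 | "The research team will communicate on an ongoing weekly basis to discuss any issues that may arise" | Contact within the team, not with the home |
| 16.0 | Withdrawal when the home's medical staff advise it | Advice runs from the home to the team, not the reverse |

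**Step 3: the same event heard by the PI.** The PI gives the depression and meaning-in-life scales at three time points. A statement made there meets the same 19.0 wording. Whether any scale item asks about suicide cannot be judged from the documents, and the point does not depend on it.

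**Result.** One sentence, in 19.0, literally covers the event without exception. None of the six places that might supply a route states a trigger for contacting the home's clinicians or gives permission to tell them.

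**The case against.** The best case for the plan has four parts.

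- **Keeping information from staff is deliberate.** Section 4.0 explains that residents depend on staff and may feel coerced. This stands, and it is why the exception should be narrow.
- **The deciding text may be elsewhere.** The consent form, the written agreements between team and participants, and the consent procedure cited in 21.0 were not available. Section 19.0 itself points to an attachment. This stands too, and limits the finding to the protocol body.
- **13.0 and 29.0 presuppose contact with the home.** They do suggest that intention, but they do not reconcile it with 19.0.
- **Licensed professionals would act anyway.** Probably so. That lowers the risk but does not correct the text.

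A reader might also infer more than the documents support.

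- **That the team is banned from referring anyone.** Section 4.0 restricts scores only, 20.0 concerns access to records, and 19.0 has a narrower reading. What is missing is an exception and a route.
- **That up to a week could pass before anyone acts, because team contact is weekly.** Section 29.0 sets no limit on contact, and 13.0 has the PI supervising the RAs. The delay assumes that an RA stays silent.
- **That two RAs could respond differently and so bias the comparison of homes.** Section 10.0 gives each RA six residents in each home, which balances the RAs across homes, and one PI oversees both.
- **That any marked worsening of mood should trigger referral.** The documents do not define such a state. Section 10.0 gives a depression cut-off of 5 or more, but ties no action to it.

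**Conclusion.** The point holds in a limited form. Section 19.0 states non-disclosure to families and staff without exception, 20.0 repeats no limit to residents, and 15.0 supplies no procedure. The protocol body therefore has no stated route to the home's clinicians for a voiced suicidal thought or intent to self-harm.

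Its size cannot be put as a number of events, because the documents give no rate. The wording covers every enrolled resident, 20 to 24 in all. The conclusion assumes the literal reading of 19.0 and is confined to the text supplied. If the consent form or attached agreements already state a limit, what remains is an inconsistency to align. Given that possibility, and the professional background of the team, this is a modest-priority correction held with moderate confidence. It is worth making because it is cheap and the event, though unquantified, is serious.

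**What to change.** Add to 15.0 and 19.0, with a matching sentence in 20.0 and in the consent form:

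> Exception: an RA who hears a suicidal thought or intent to self-harm tells the PI at once. The PI assesses the resident the same day and informs NH clinical staff of the concern, not the score or the story. Date, home and action are logged by ID.

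The PI takes the same steps after hearing such a statement directly. Leave 4.0 as it is. Mention the limit at the consent reviews that 21.0 already schedules, at the first visit and at post-test 1. If the consent form already states a limit, bring 19.0 and 20.0 into line with it.

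For the analysis, apply the rule in both homes and keep referred residents in the MANCOVA as allocated wherever post-test data exist. Once alerted, medical staff may advise withdrawal under 16.0, so some post-tests may be missing. Report referrals and resulting withdrawals by home. With 10 to 12 residents per home, one withdrawal is 1/12 = 8.3% to 1/10 = 10% of a home. That describes home size, not expected harm, but it is reason enough to report each one.

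The cost is a short protocol paragraph and a consent sentence, through an IRB modification of the kind that 11.0, 29.0 and 30.0 already expect, plus one same-day assessment by the PI per event. The downside is a small, disclosed limit to confidentiality towards staff on whom residents depend, and possibly less open answers.
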